16.5.9 Aim 5 Expected Output

These analyses will provide us with the following new insights into APS conditions:

- How patient comorbidities differ across previously described subphenotypes and newly identified subphenotypes
- How patient exposures (tobacco, alcohol, air pollution) differ across previously-described subphenotypes and newly identified subphenotypes; whether patient exposures represent a “treatable trait” that modulate patient risk for clinically unfavorable heterogeneity
- How biophysical constitution (as assessed using body composition and integrative functional assessments) contributes to acute and long-term trajectories of APS conditions
- How these contributing factors interact with common ICU interventions (corticosteroids, neuromuscular blockade, early mobilization and antibiotics) as related to acute and long-term outcomes

16.6 Appendix F (Aim 6): Develop approaches for translating phenotypes to the bedside to enable follow-on precision clinical trials.

16.6.1 Aim 6 Background and Rationale

ARDS, sepsis, and pneumonia cause severe morbidity and mortality globally. While supportive care has improved outcomes over the last decades, persistently high morbidity and mortality indicate that new treatments are needed. Unfortunately, the history of trials in ARDS, sepsis, and pneumonia has been disappointing. At most 5% of Phase 3 trials in critical care demonstrate efficacy,¹⁻³ even in settings where pre-clinical data has been promising.^{4,5} This finding is likely due to improperly specified target populations, inadequate predictive enrichment, and inappropriate trial endpoints.⁶⁻⁹

Robust statistical/machine-learning techniques hold promise for the definition of relevant subgroups of patients within complex syndromes. Such subgroups may include modifiable biological pathways (e.g., fibrosis and repair), an influential polymorphism (e.g., IL-6 promoter),¹⁰ a comorbidity (e.g., diabetes mellitus), or an important social context (e.g., economic deprivation). Identification of such subgroups holds promise as the foundation of a subsequent generation of targeted therapeutics.

The focus in this appendix is on phenotypes as actionable target populations—i.e., homogenous, treatment-responsive subgroups of patients identifiable at the time a treatment decision must be made. We do so recognizing that such phenotype identification has improved clinical care in, e.g., pulmonary hypertension¹¹ and asthma.¹² Multiple analytic aspects are important to accomplishing the ultimate goal in this appendix of designing high-quality trials in the right target populations within ARDS, pneumonia, and sepsis, with higher probability of success.

Logistically, the use of phenotypes as actionable target populations includes two critical components.

The first component is the ability to identify phenotype membership at the time a treatment decision must be made. Usual phenotyping methods are based on high-dimensional data in the derivation and validation cohorts and cannot be straightforwardly applied in clinical practice. In order to be used in clinical practice, simpler, parsimonious definitions are required. These parsimonious models utilize a restricted set of variables—all of which can be obtained clinically—to identify phenotype membership in real time. Treatment decisions can then be made based upon the phenotype assignments of the parsimonious models. Substantial progress in machine learning, combined with the richness of the APS Consortium cohort dataset, makes possible the development and validation of such classification rules for application in future trials.

The second component is to identify the most promising future trial candidates in ARDS, pneumonia, and sepsis, whether repurposed agents (i.e., those already in clinical use among patients enrolled in the APS Phenotypes Consortium cohort) or hypothetical novel agents (i.e., the expected effect of modulating a protein biomarker or other biological signal among Consortium patients). Fortunately, statistical methods for causal inference and observational data methods allow for the performance of simulated clinical trials in a way that has been demonstrated to closely approximate inferences drawn from prospective randomized trials.¹³ These methods of “target trial emulation” provide the opportunity to make key observations relevant to the design and conduct of future clinical trials.¹⁴

16.6.2 Aim 6 Study Objectives

Primary Objective (Aim 6):

Aim 6a. Perform target trial emulations of observed or potential novel therapies, with prespecified assessment of possible treatment effect heterogeneity. As an illustrative example of one such emulation, we will estimate the effect of a potential DAMP-blocking agent administered to lower DAMP to the below the median level versus usual care alone on all-cause mortality at 60 days. The baseline historic syndrome (ARDS, pneumonia, or sepsis) will be the primary subgroups for treatment effect heterogeneity.

Aim 6b. Derive and validate parsimonious classification rules using clinically available baseline data to assign patients to APS-identified phenotypes.

Exploratory Objectives (Aim 6):

Aim 6a:

- Assess treatment effect heterogeneity within target trial emulations based on (a) the hyper- vs. hypo-inflammatory phenotypes identified by Calfee and colleagues and (b) novel phenotypes identified within the APS Consortium
- Assess secondary endpoints for the target trial emulation, including mortality at 30- and 90-days, ICU-free days, organ-support-free days, WHO ordinal outcome scale, and the 12-month outcomes measured among the long-term outcome cohort within the APS Consortium.

Aim 6b:

- Compare the accuracy of (a) classification rules restricted to currently available clinical values with (b) classification rules that incorporate results that could feasibly be reduced to clinical application (e.g., cytokine results that could be performed at the point of care).

16.6.3 Aim 6 Study Population

All enrolled APS Phenotypes Consortium cohort patients

16.6.4 Aim 6 Study Design

No additional laboratory procedures will be performed for this Aim.

Objective 1 will be approached using statistical learning classification models based on clinically available data and/or parsimonious biological data, we will derive and validate classification models, with an intraclass correlation coefficient (ICC) ≥ 0.75 .

Objective 2 will be approached using treatment normalization, causal inference, and design of simulated trials using structured design deliberations and target trial emulation techniques. Using these methods, we

will define and perform 5 high-priority trial simulations. Results of those simulated trials will be reported back to the Steering Committee and NIH.

16.6.5 Aim 6 Study Procedures

No additional non-statistical procedures will be performed for this aim beyond those in the main protocol and the Appendices that generate biomarker data.

16.6.6 Aim 6 Data, Images, and Biospecimens Used from the APS Consortium

All data, with the exception of biomarkers or other biological assays (e.g., microbiome) that are not expected to be reducible to a clinically relevant turnaround time (i.e., biomarkers or other biological assays that would take >24h to return results). These data centrally include (1) medications and other therapies (e.g., respiratory support modes) for simulated trials of repurposed medications and (2) protein biomarkers and other biological assays (e.g., transcriptomic results given recent progress in turn-around times for peripheral blood RNA sequencing) for simulated trials of potential novel agents that modulate a given biological signal. The biomarkers and other bioassays proposed in the APS Phenotypes Consortium cohort Aims have been chosen on the basis of their expected causal roles in ARDS, pneumonia and sepsis pathophysiology. It is therefore anticipated that the output of simulated trials of potential novel agents will be highly relevant to the development and design of future clinical trials.

16.6.7 Aim 6 Adequacy of sample size

The statistical approaches that will be used in the ultimate analysis will be specified *a priori* in a Statistical Analysis Plan. Here, we provide an assessment of the adequacy of the sample size based on reasonable assumptions, recognizing that the final methods will be highly optimized using rapidly developing methodology.

For Objective 1, historically, formal sample size calculations have not been performed for classification problems such as these, with general reliance on heuristics (e.g., 5–7 observations per variable in the classification problem). Nevertheless, Walter’s method¹⁵ makes possible a power estimate based on comparisons against a null hypothesis for ICC. In this case, an overall sample size of 460 provides approximately 90% power to detect an ICC difference of 0.05 against a null hypothesis of 0.70, 80% with a null of 0.60, and 70% with a null of 0.50. (Note that this sample size refers to the cohort size for all phenotypes for a given phenotyping problem, rather than the size of any individual phenotype within the overall cohort.)

For Objective 2, the overall sample size of 4,000 is 2.5–10 times larger than other prospective phenotyping efforts in this disease area. Recognizing the complexities of the data and associated analyses, power estimates by simulation would be heavily assumption-laden. We focus here on power associated with trial emulation. A conservative assessment of power can be determined by considering inference about the weighted average causal effect obtained using matching weights.¹⁶

This approach mimics 1:1 propensity score matching and emphasizes trials that enroll participants whose propensity scores are close to 0.5.¹⁶ This is consistent with the goal of trial emulation, as patients with propensities close to 0.5 represent patients for whom greater equipoise exists. Using the analogue to 1:1 matching, we can estimate the minimum detectable treatment effects, based on the sample size of the

smaller of the two comparison groups (Table 14). The table rows apply either to the full cohort or to a subgroup of interest when evaluating treatment effect heterogeneity.

16.6.7 Aim 6 Statistical Analysis

As noted for other aims, following the principles laid out in the protocol, each analysis will be pre-specified in an SAP. When an optimal approach is not clear, different methods may be compared; comparison of different approaches will be a strong contribution to the methods literature. Below, we outline the general direction that we plan to undertake to accomplish this aim.

For Objective 1, we plan to first pursue a dimension reduction exercise (e.g., penalized regression) to identify the variables most likely to identify class membership. The next step will be use of a machine learning technique (e.g., classification and regression trees) to derive the classification rule. Validation can be performed by assessment of the ICC, comparing the underlying phenotype assignment with the classification generated by the classification rule.

For Objective 2, a rigorous, multi-stage method will be employed to minimize bias and maximize the probability of accurate inference. The key features of the multi-stage method are treatment normalization, phenotype identification, phenotype assignment (e.g., using the methods of Objective 1), definition and prioritization of simulated trials, and the actual performance of the simulated trials. The phases of analysis are displayed in Table 14.

Table 14. Aim 6: Flow of analysis for Objective 2.

Step	Task	Methods	Output
A1	Account for the role of treatment in characterization of phenotypes	Normalize disease trajectories via dynamic treatment regime and inverse probability weighting	A normalized pseudo-cohort for phenotyping
A2	Identify disease phenotypes using longitudinal data	Hidden Markov Models and machine-learning techniques	3–5 distinct disease phenotypes
A3	Predict disease phenotypes for individual patients	Elastic net multinomial regression	Patient-level probabilities of phenotype membership
A4	Define and prioritize trial emulations	Structured Steering Committee review of phenotype attributes and potential treatments	Prioritized list of ≤ 5 trial emulations
A5	Identify efficacy signals for treatments among phenotypes	Target trial emulations with exploration of treatment effect heterogeneity by phenotype	Results of trial emulations, by phenotype

Treatment normalization is a crucial initial step, given the risk that variations in treatment may shape the measured features for phenotyping, independent of the patient’s acute biology and premorbid status. Treatments may change over time, and their effect may similarly vary over time. Thus, for example, glucocorticoids decrease inflammatory biomarkers,¹⁷⁻¹⁹ while low-tidal volume ventilation decreases

inflammatory markers, including interleukin-6.²⁰ Failure to control for the dynamic effect of treatment would thus introduce severe bias, motivating techniques to control for treatment over time. Treatment normalization generates a reweighted cohort on which the relevant phenotyping (and phenotype assignment; steps A2–A3) are performed. After the results of these initial steps, a structured deliberation at the Steering Committee level (step A4) before performance of simulated trials will minimize the risk of alpha inflation (i.e., false positive inferences from simulated trials). The performance of simulated trials (step A5) will follow valid techniques for causal inference, including appropriate cohort definition and simulated treatment plus adjustment for propensity to receive the treatment. For repurposed medications, the treatment definition is simple and familiar—the treatment actually received by the patient in the cohort. In addition to repurposed medications, the simulated trials are able to include assessment of potential novel treatments. For simulated trials of potential novel treatments, levels of measured biomarkers are used as surrogates for treatments that could modulate a biomarker level by a certain level (e.g., assess a hypothetical agent that would lower plasma levels of sRAGE by 50%). Continuous-variable approaches to treatment and treatment adjustment are used to support these analyses for hypothetical novel treatments.^{21,22} Note that where a given phenotype has a valid classification rule (as developed in Objective 1), that classification rule will be used for the simulated trials to improve generalizability.

16.6.8 Aim 6 Adequacy of sample size

The statistical approaches that will be used in the ultimate analysis will be specified *a priori* in a Statistical Analysis Plan. Here, we provide an assessment of the adequacy of the sample size based on the approach described above, recognizing that the final methods will be highly optimized using rapidly developing methodology.

As described in the rationale for the cohort sample size, formal sample size calculations have traditionally not been performed for classification problems such as these, with general reliance on heuristics (e.g., 5–7 observations per variable in the classification problem). We have shown that with the overall sample size of 4,000, cluster analyses with as many as 500 features are feasible. As well as the approach described in the sample size justification, Walter’s method¹⁵ makes possible a power estimate based on comparisons against a null hypothesis for ICC – the ICC is used as a measure of concordance between actual and predicted class membership with a high ICC reflecting good concordance. Sample sizes calculated in this way are consistent with sample sizes based on the correlation coefficient or detectable difference approach; an overall sample size of 460 provides approximately 90% power to detect an ICC difference of 0.05 against a null hypothesis of 0.70, 80% with a null of 0.60, and 70% with a null of 0.50.

For objective 2, we focus on power associated with trial emulation. A conservative assessment of power can be determined by considering inference about the weighted average causal effect obtained using matching weights.¹⁶ This approach mimics 1:1 propensity score matching and emphasizes trials that enroll participants whose propensity scores are close to 0.5.¹⁶ This is consistent with the goal of trial emulation, as patients with propensities close to 0.5 represent patients for whom greater equipoise exists. Using the analogue to 1:1 matching, we can estimate the minimum detectable treatment effects, based on the sample size of the smaller of the two comparison groups (Table 15). The table rows apply either to the full cohort or to a subgroup of interest when evaluating treatment effect heterogeneity, and show that small to modest differences can be observed even in the smaller subgroups.

Table 15. Aim 6: Minimum detectable average treatment effect (90% power, 2-sided $\alpha = 0.05$)

Evaluable patients in smaller group (N)	Detectable mean difference in continuous outcome (% SD)	Detectable % reduction in hazard ratio		
		10% of pts with events	20% of pts with events	40% of pts with events
200	32.5%	64.1%	51.5%	40.1%
400	22.9%	51.5%	40.1%	30.4%
800	16.2%	40.1%	30.4%	22.6%
1200	13.2%	34.2%	25.6%	18.9%

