16.6.9 Aim 6 Expected Output

The expected output from Objective 1 is a classification rule for each major phenotyping task for which ≥ 460 overall patients are available. These classification rules can be immediately applied to future patient populations for future trials.

The expected output from Objective 2 is a suite of simulated trials of repurposed and/or hypothetical novel therapies. These trials would be used to motivate and to design next-generation trials in ARDS, pneumonia, and sepsis.

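### Aim 6, Objective 1: 460 patients do not give the stated 90/80/70% power when two classifications per patient are compared; the figures are about 73/55/43% (one-sided 5%) or 62/42/32% (two-sided 5%)

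*Protocol*

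**What the plan says.** Aim 6 Objective 1 derives parsimonious rules that assign patients to phenotypes. Section 16.6.4 sets the target: "we will derive and validate classification models, with an intraclass correlation coefficient (ICC" of at least 0.75.

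The power statement is in Section 16.6.8, and the same figures appear in the Aim 6 adequacy section numbered 16.6.7. Walter's method "makes possible a power estimate based on comparisons against a null hypothesis for ICC", and "an overall sample size of 460 provides approximately 90% power to detect an ICC difference of 0.05 against a null hypothesis of 0.70", then "80% with a null of 0.60, and 70% with a null of 0.50".

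Two places say what is compared. Section 16.6.8: "the ICC is used as a measure of concordance between actual and predicted class membership". The section headed 16.6.7 Aim 6 Statistical Analysis: "Validation can be performed by assessment of the ICC, comparing the underlying phenotype assignment with the classification generated by the classification rule". No third rating is mentioned, and no alpha or sidedness is given for this test. The only alpha stated for Aim 6 is the two-sided 0.05 of Table 15, which concerns Objective 2.

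Section 16.6.8 adds that sample sizes obtained this way agree with those from a correlation-coefficient or detectable-difference approach. Section 16.6.9 then uses the number as a threshold: "The expected output from Objective 1 is a classification rule for each major phenotyping task for which" at least 460 patients are available.

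**The concern.** In Walter's method the information per patient rises with the number of ratings, so a patient count has no power attached until that number is fixed. The text fixes it at two. The stated power looks too high for two.

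The figure of 460 does work in the plan: it marks which phenotyping tasks are expected to yield a rule. If the power behind it is overstated, a task near that size has a larger chance of failing to show that a rule with the target ICC of 0.75 beats 0.70 than the protocol tells its readers.

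A second question is whether an ICC suits a nominal class label. With three or more unordered classes, an ICC computed on class numbers can change when the classes are renumbered, and Section 16.6.4 sets a cut on that scale.

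**Working it through.** **Inputs.** Patients k = 460; null ICCs 0.70, 0.60 and 0.50; difference 0.05; stated power 90/80/70% (Section 16.6.8). Ratings per patient n = 2 (Sections 16.6.7 Statistical Analysis and 16.6.8). Alpha is not stated, so one-sided 0.05 and two-sided 0.05 are both shown as assumptions.

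**Formula.** With t = ICC/(1 − ICC) and C = (1 + n·t0)/(1 + n·t1), power = Φ( √[(k − 1)(n − 1)(ln C)²/(2n)] − z ).

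**Two ratings.** (k − 1)(n − 1)/(2n) = 459/4 = 114.75.

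| Null → alternative | C | (ln C)² | Square root term | Power, z = 1.645 | Power, z = 1.960 |
|---|---|---|---|---|---|
| 0.70 → 0.75 | 5.667/7 = 0.8095 | 0.04465 | 2.264 | 73.2% | 61.9% |
| 0.60 → 0.65 | 4/4.714 = 0.8485 | 0.02700 | 1.760 | 54.6% | 42.1% |
| 0.50 → 0.55 | 3/3.444 = 0.8710 | 0.01909 | 1.480 | 43.4% | 31.6% |

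The exact F-test gives the same to within 0.1 percentage point.

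**Can the stated figures be reproduced?** Yes, but not with two ratings:

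- n = 4, one-sided 0.05: 91.4/78.6/69.2%.
- n = 7, two-sided 0.05: 91.7/78.8/70.3%.
- n = 3, one-sided 0.05: 86.8/71.1/60.3%; n = 5: 93.6/82.6/74.4%. Neither fits all three values.
- n = 2, one-sided 0.10: 83.7/68.4/57.9%. To match the stated triple with n = 2, the one-sided alpha would have to be about 0.16 to 0.18.

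**The protocol's own cross-check.** For a correlation tested by Fisher's z with 460 patients at null 0.70: atanh(0.75) − atanh(0.70) = 0.1057; times √457 = 2.259; minus 1.645 = 0.614; power 73.0%. The other two nulls give 54.4% and 43.3%. The correlation approach therefore agrees with the two-rating result, not with 90/80/70%.

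**Patients needed with two ratings.** k = 1 + 2n(zα + zβ)²/[(n − 1)(ln C)²]. For 90% power at null 0.70:

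- One-sided: 1 + 4 × (1.645 + 1.282)²/0.04465, giving 769.
- Two-sided: 1 + 4 × (1.960 + 1.282)²/0.04465, giving 943.

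**Power at larger samples (two ratings, null 0.70).** 600 patients: 82.7% one-sided, 73.4% two-sided. 700: 87.5% and 79.8%. 1,500: 99.3% and 98.3%.

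**ICC on class numbers.** Take three equal classes coded 1, 2, 3, with two of them exchanging 30% of their members. That is 20% of all patients, so accuracy is 80% and kappa is (0.80 − 1/3)/(2/3) = 0.70. The label variance is 2/3, and the ICC is approximately 1 − (mean squared difference/2)/(2/3).

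- Exchanging classes numbered 1 apart: 1 − (0.20 × 1/2)/(2/3) = 0.85.
- The same two classes numbered 2 apart: 1 − (0.20 × 4/2)/(2/3) = 0.40.
- The same 20% error spread evenly over the three pairs (mean squared difference per error = (1 + 1 + 4)/3 = 2): 1 − (0.20 × 2/2)/(2/3) = 0.70, equal to kappa under any numbering.

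With two classes, renumbering changes nothing.

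**The case against.** The strongest reply is that nothing is planned at 460. Aim 6 draws on all enrolled patients, with a target of 4,000. The phenotyping samples the protocol names are 1,500 for Aim 2, 1,500 ventilated patients with syndrome subgroups down to 600, and 700 with NBBAL (Sections 16.2.3 and 16.3.8). The null that goes with a target of 0.75 is 0.70, the best case of the three. This stands, and it limits the severity.

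It can also be said that the methods are provisional, with validation by ICC offered as one possibility and the details left to the statistical analysis plan. That excuses the choice of measure, but not a power figure and a threshold that the protocol states as results. Section 16.6.8 also leans on a cohort sample size rationale that is not in the text available here, so its assumptions could not be checked. The comparison it describes is still two-way.

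On the ICC, the protocol never says it will be computed on class numbers. The range of 3 to 5 phenotypes belongs to Objective 2 (Table 14), although the Objective 1 rules are carried into those emulations. The previously defined examples in Table 12 are all two-class. The 0.40 versus 0.85 contrast needs errors concentrated between two classes. All of this stands, so the ICC point is conditional and secondary.

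**Conclusion.** The stated power is wrong for the comparison described. At 460 patients it is overstated by about 17, 25 and 27 percentage points at one-sided 5%, or 28, 38 and 38 at two-sided 5%. The conclusion rests on two ratings per patient, which the text gives, and on an assumed alpha, which it does not. The stated agreement with the correlation approach also fails.

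A reader might infer more than the documents support:

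- That the figures assumed four ratings. Four fits only at one-sided 5%, and seven fits at two-sided 5%. Since alpha is unstated, the source of the error cannot be identified.
- That poor rules will be accepted because of the 460 figure. Low power makes a good rule harder to confirm; it does not let a poor one through.
- That the ICC is invalid for Aim 6 altogether. The objection holds only for numeric coding of three or more unordered classes with unevenly distributed errors.
- That Aim 6 as a whole is underpowered. At the named sample sizes, power at null 0.70 is 83% (one-sided) or 73% (two-sided) at 600 and above 98% at 1,500, provided the whole sample enters the ICC.

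Severity: should be fixed. The threshold and its justification are wrong as written, but the planned samples exceed it.

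**What to change.** In both Aim 6 adequacy sections, state that there are two ratings per patient, state alpha and sidedness, and give the power at 460 as about 73/55/43% (one-sided 5%) or 62/42/32% (two-sided 5%). Remove or correct the remark about agreement with the correlation approach.

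In Section 16.6.9, choose one of two courses. Either keep 460 and present it with that lower power, or, if 90% power at null 0.70 is to be the basis, change it to 769 (one-sided) or 943 (two-sided). The second course puts the 600- and 700-patient samples below the threshold.

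For rules with three or more unordered phenotypes, replace the ICC in Sections 16.6.4 and 16.6.7 Statistical Analysis by a label-invariant measure such as unweighted kappa, with class-specific sensitivity, and restate the 0.75 cut and the sizing for that measure; 769 and 943 apply only to the ICC. Cohen's kappa is already named in Section 16.3.7 for concordance between phenotypes. Two-class rules need no change of measure.

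The cost is wording. No data collection changes; the price is a less favourable stated power or fewer tasks that meet the threshold.

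### Table 15 gives detectable treatment effects within one cohort or subgroup, not differences between subgroups, and its hazard columns contradict the small-to-modest conclusion drawn for smaller subgroups

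*Protocol*

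**What the plan says.** Section 16.6.2 makes heterogeneity part of the primary objective of Aim 6a: target trial emulations are to be done "with prespecified assessment of possible treatment effect heterogeneity". The baseline syndromes (ARDS, pneumonia, sepsis) are the primary subgroups, and the illustrative endpoint is 60-day all-cause mortality.

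Section 16.6.8 explains how the power table was built: "Using the analogue to 1:1 matching, we can estimate the minimum detectable treatment effects, based on the sample size of the smaller of the two" (that is, whichever treatment arm has fewer patients). It then says how to use it: "The table rows apply either to the full cohort or to a subgroup of interest when evaluating treatment effect heterogeneity". The sentence ends with the conclusion that the rows "show that small to modest differences can be observed even in the smaller subgroups". The section numbered 16.6.7 Aim 6 Adequacy of sample size also says that the rows apply to a subgroup when heterogeneity is evaluated.

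Table 15 is titled as a minimum detectable average treatment effect at 90% power and two-sided alpha 0.05. Its columns are N in the smaller group, the mean difference as a percentage of the SD, and the hazard reduction when 10%, 20% or 40% of patients have events. The two smallest rows are "200 32.5% 64.1% 51.5% 40.1" and "400 22.9% 51.5% 40.1% 30.4".

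**The concern.** Two things do not fit together. First, heterogeneity is a difference between treatment effects in different subgroups. A table of average effects within one group does not say how large that difference must be to be found, yet it is the only power material offered for heterogeneity. Second, the conclusion about smaller subgroups does not match the hazard figures printed below it, and a mortality endpoint would use those columns.

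Heterogeneity by syndrome belongs to a primary objective, step A5 in Table 14 extends it to phenotypes, and section 16.6.9 says that the emulations will be used to motivate and design later trials. A reader who takes the table as power for heterogeneity could read a non-significant contrast as evidence of a common effect. The same reader could take significance in one subgroup and not in another as a phenotype-specific effect.

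**Working it through.** **Inputs.** Power 90%, two-sided alpha 0.05, 1:1 comparison, N in the smaller group, and event shares of 10%, 20% and 40% (section 16.6.8, Table 15). Mortality estimate 30% (section 16.2.8, Aim 2). The sum of normal quantiles is 1.960 + 1.282 = 3.2415 before rounding.

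**Step 1: reproduce Table 15.**
- Continuous outcome: detectable difference = 3.2415 × √(2/N). At N=200 this is 32.4% of an SD (32.5% with the t distribution).
- Hazard (Schoenfeld): events D = 2N × event share, and HR = exp(−3.2415 × 2/√D). At N=200 and 10% events, D = 40 and HR = exp(−1.025) = 0.359, a reduction of 64.1%.

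All 16 cells agree to within 0.1 percentage point. The cells are therefore two-group effects inside a single cohort or subgroup of 2N patients.

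**Step 2: the hazard columns against the conclusion.** At N=200 the required hazard ratios run from 0.36 to 0.60 (reductions of 64.1% to 40.1%). At N=400 the reductions are 51.5% to 30.4%. With 30% events:
- N=200: D = 120, reduction 44.7%
- N=400: D = 240, reduction 34.2%
- N=800: D = 480, reduction 25.6%
- N=1200: D = 720, reduction 21.5%

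**Step 3: a contrast between two disjoint subgroups.** The two effect estimates are independent, so their variances add. With the same event share in both, the detectable contrast on the log-HR or SD scale is the smaller subgroup's tabulated value multiplied by √(1 + N_small/N_other). For equal subgroups this is √2 = 1.41:

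| N in each subgroup | Within one subgroup: % SD; hazard reduction at 10/20/40% events | Between two equal subgroups: % SD; reduction in ratio of HRs at 10/20/40% events |
|---|---|---|
| 200 | 32.4; 64.1/51.6/40.1 | 45.8; 76.5/64.1/51.6 |
| 400 | 22.9; 51.6/40.1/30.4 | 32.4; 64.1/51.6/40.1 |
| 800 | 16.2; 40.1/30.4/22.6 | 22.9; 51.6/40.1/30.4 |
| 1200 | 13.2; 34.2/25.6/18.9 | 18.7; 44.7/34.2/25.6 |

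Power for a contrast as large as the tabulated effect is Φ(3.2415/1.414 − 1.960) = Φ(0.332), about 63%.

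**Step 4: unequal subgroups.** The factor falls as the comparator grows. For N=200 against 800 it is √1.25 = 1.12. For 200 against 1200 it is √1.167 = 1.08, so the N=200 row becomes about 35% of an SD and 67/54/43%. The factor never reaches 1.

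**The case against.** The strongest reply is that the table is honestly labelled. Its title says average treatment effect, it is sized on the smaller comparison group, its rows refer to one cohort or one subgroup, and nowhere does the text mention an interaction test. Every detectable value is printed, so nobody is misled about its size. Most of this stands. A reader might infer that the protocol expressly claims power for an interaction test, and it does not. What remains is that the rows are tied to evaluating heterogeneity, a favourable conclusion is drawn from them, and no between-subgroup figure is given.

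Other stronger readings also fail:
- **That Table 15 is miscalculated.** It is not; every cell reproduces.
- **That the contrast is always at least 1.41 times larger.** For disjoint subgroups with the same event share, 1.41 is the ceiling relative to the smaller subgroup's row.
- **That 76.5/64.1/51.6% is this design's sensitivity across ARDS, pneumonia and sepsis.** Those groups overlap (section 7.2.2 expects nearly all pneumonia patients to meet Sepsis-3), their minimum targets are unequal (1000, 2000 and 2000), and Table 14 expects 3 to 5 phenotypes. The equal-split figures are only an illustration.
- **That the small-to-modest wording is wrong throughout.** It is fair for the continuous column, and several secondary endpoints, such as ICU-free days, are not hazards. The 64.1% cell is also the worst case, at N=200 with 10% events.

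It is also true that section 12.2.4 suggests interaction-with-treatment terms when clusters are used to study differential treatment effect, that phenotype-based heterogeneity is labelled exploratory, and that step A4 limits the emulations to five. A later analysis plan may well test heterogeneity properly. None of this corrects the statement of power in section 16.6.8, which this protocol makes itself.

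**Conclusion.** Wrong as written, as a matter of stated power and its interpretation rather than of arithmetic. For time-to-event outcomes the conclusion about smaller subgroups is contradicted by the table's own rows: reductions of 40.1% to 64.1% at N=200 and 30.4% to 51.5% at N=400, or about 45% and 34% at 30% mortality. This part needs no assumption beyond the protocol's own, except that the 30% figure is borrowed from Aim 2.

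For heterogeneity, the table overstates sensitivity for any split into disjoint subgroups. How far depends on relative size: a factor of √(1 + N_small/N_other), which is 1.41 for equal subgroups and less against a larger comparator. This assumes independent subgroups, the same event share and the same 1:1 approximation as Table 15. Exact figures for the overlapping syndromes cannot be derived from the document.

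**What to change.** In section 16.6.8, and where section 16.6.7 Aim 6 Adequacy of sample size repeats the statement:
- Label Table 15 as detectable effects within the cohort or within one subgroup, and state that it does not give power for treatment effect heterogeneity.
- Add a few illustrative detectable contrasts for disjoint subgroups, such as syndrome present against absent, with the assumed subgroup sizes and event share stated. A blanket 1.41 multiplier should not be used.
- Confine the small-to-modest wording to the continuous outcome, or replace it with the hazard figures for the smaller rows.

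The cost is a relabelled table, a short addition and one rewritten sentence. Sample size, data collection and the planned analyses are unaffected; the stated power becomes less favourable.
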